2 INTRODUCTION

2.1 Study Rationale

MK-5720 is a novel ester carbamate acetal prodrug of the PDE10A inhibitor MK-8189 and is being developed as a LAI formulation of MK-8189 for the QM treatment of schizophrenia. The primary bioconversion pathway involves systemic esterase-mediated hydrolysis of MK-5720 to the metabolite, MK-8189. MK-8189 is a potent and highly selective competitive inhibitor of PDE10A that is being developed as an orally administered, novel therapeutic for the treatment of schizophrenia. MK-5720 and its metabolite, MK-8189, are not considered compounds with a high potential for risk of harm to schizophrenic participants based on preclinical safety data available for MK-5720 and the clinical safety experience gathered across multiple clinical studies conducted with oral MK-8189 to date. No dose-limiting toxicities were observed in the 1-month rat and rhesus toxicity studies with MK-5720 and substantial preclinical safety margins were obtained over initial human doses. Preclinical studies with MK-5720 as well as clinical safety experience observed with MK-8189 in schizophrenic patients to date support the study of MK-5720 in participants with schizophrenia for the FIH study.

This study constitutes the first administration of MK-5720 to humans. The main objective of this FIH study is to evaluate the safety, tolerability, and PK of MK-5720 LAI after administration of single-IM doses in adult participants with schizophrenia. Since the developmental and reproductive toxicological data for MK-5720 has not been generated at this stage, the potential effect of MK-5720 in reproductive healthy women is unknown. As a result, only healthy men and PONCBP, ages 18 to 60 years of age inclusive, who meet the inclusion criteria are eligible to participate in the study. Data from this study will be used to guide the selection of doses and dosing regimens for upcoming clinical studies in patients with schizophrenia.

The number of participants in each panel (n=8 to 12, allocated n=6 to 9 to MK-8189/MK-5720 and n=2 to 3 to placebo) was chosen for this early Phase 1 study to balance scientific requirements for statistical significance with the study's objectives regarding the ethical use of human participants in a clinical study.

Details regarding specific benefits and risks for participants in this clinical study may be found in the accompanying IB and ICF documents.

2.2 Background

Refer to the IB/approved labeling for detailed background information on MK-5720.

2.2.1 Pharmaceutical and Therapeutic Background

MK-5720 is a novel ester carbamate acetal prodrug of the PDE10A inhibitor, MK-8189 and is being developed as a LAI formulation of MK-8189 for the QM treatment of schizophrenia. MK-8189 is a potent and selective inhibitor of PDE10A that is being developed as a novel therapeutic for the treatment of schizophrenia. The PDE10A enzyme metabolically

inactivates the ubiquitous second messengers, cAMP and cGMP [Bender, A. T. and Beavo, J. A. 2006] and is highly expressed in the target nucleus of the corticostriatal pathway, the striatum [Seeger, T. F., et al 2003].

Preclinical pharmacology studies demonstrate that PDE10A inhibition increases cAMP/cGMP signaling in pathways that have been associated with underlying pathology (glutamate) as well as clinically validated therapeutics (dopamine D2 receptor antagonists) for schizophrenia. Enhanced signaling in these pathways is hypothesized to restore behavioral inhibition that is impaired in schizophrenia [Grauer, S. M., et al 2009] [Schmidt, C. J., et al 2008]. PDE10A inhibitors may potentially be an alternative treatment as monotherapy and/or adjunct treatment in schizophrenia patients who have inadequate response to first line AAP or SGA treatment.

2.2.2 Preclinical and Clinical Studies

2.2.2.1 Preclinical Studies with MK-5720

MK-5720

Refer to the IB for detailed preclinical information on MK-5720.

2.2.2.2 Clinical Studies with MK-5720 and MK-8189

MK-5720

There have been no clinical studies conducted with MK-5720.

MK-8189

Preclinical and clinical study information can be found in the MK-8189 IB.

Summary of Completed Phase 1 Clinical Studies

Three single-dose clinical studies (P001, P002, and P004) in healthy participants, a single-dose study in healthy participants and participants with moderate hepatic impairment (P012), 2 CYP3A DDI studies in healthy participants (P006, P015), and 4 multiple-dose clinical studies in participants with schizophrenia and healthy participants (P003, P007, P011, and P016) have been completed with MK-8189. P011 included elderly (>60 years of age, n=12) participants with schizophrenia and healthy elderly (>60 years of age, n=18) participants. Overall, across the completed studies, 231 participants have received at least one dose of MK-8189; 124 participants without schizophrenia and 107 participants with schizophrenia.

Overview of MK-8189 Pharmacokinetics

CCI

Median Tmax of MK-8189 as monotherapy ranged from 10 to 24 hours with a t1/2 of approximately 10.9 hours CCI

CCI

MK-8189 is a CYP3A substrate and in a DDI study (P006), the coadministration of extended release 240-mg diltiazem, a moderate CYP3A inhibitor, increased MK-8189 AUC and Cmax by approximately 2-fold and 1.27-fold, respectively. Additionally, a subsequent DDI study (P015) demonstrated that coadministration of itraconazole, a strong CYP3A inhibitor, increased MK-8189 AUC and Cmax by approximately 1.2-fold and 1.16-fold, respectively, and these results were generally consistent with the results observed in the diltiazem study. Collectively, these results confirm that MK-8189 is a CYP3A substrate. CCI

Overview of MK-8189 Safety Profile

In a Phase 2 POC trial (P005), MK-8189 was generally well tolerated by the 90 participants who received at least 1 dose of the once daily MK-8189 (titrated every 3 days from 4 mg to 8 mg and 12 mg, as tolerated). Participants were dosed after they were able to taper off psychotropic medications. AEs that occurred in $\geq 5\%$ of participants in the MK-8189 intervention group and had greater incidence than placebo were diarrhea, nausea, vomiting, decreased appetite, akathisia, dystonia, headache, sedation, somnolence, anxiety, and insomnia. No deaths were reported in the P005 study. No SAEs were reported for

participants on MK-8189. Eight participants (8.9%) had an AE of dystonia and 2 participants (2.2%) had an AE of oromandibular dystonia. Detailed PK and safety information from individual completed studies are summarized in the IB.

2.2.3 Completed Clinical Studies (MK-8189)

2.2.3.1 Protocol 011

P011 was a Phase 1 multiple-dose randomized, double-blind, placebo-controlled, multicenter, 2-part study. Part 1 (Panels A/B/C) evaluated the safety and tolerability of different titration regimens or initiating MK-8189 treatment without titration in participants ≤60 years of age with schizophrenia. Part 2 (Panels D/E/F/G) evaluated the multiple-dose safety, tolerability, and PK of MK-8189 in elderly participants with schizophrenia (Panel D and Panel E) and healthy elderly participants (Panel F and Panel G) between 61 and 80 years of age (inclusive). Panel E and Panel G were to explore the safety and tolerability at different titration regimens and were only to be initiated after a safety and tolerability review from Panel D and Panel F, respectively.

Part 1 Panel A: Participants with schizophrenia. Intervention MK-8189 16 mg/placebo (Days 1 to 3), 24 mg/placebo (Days 4 to 10).

Overall, multiple oral doses of MK-8189 titrated from 16 to 24 mg were generally well tolerated in participants with schizophrenia. Of the 8 participants included in the safety analysis in Panel A, 6 (75%) experienced 1 or more AEs during the study; 5 participants (83.3%) after MK-8189 and 1 participant (50%) after placebo. All AEs were mild or moderate in intensity and resolved prior to the end of the study. No participants were discontinued from the study intervention due to an AE.

Five participants (62.5%) reported 1 or more AEs that the investigator considered study intervention related; 4 participants (66.7%) after MK-8189 and 1 participant (50%) after placebo. The most commonly (>1 participants) reported study intervention related AEs were decreased appetite (n=1 [16.7%] following MK-8189 24 mg and n=1 [50.0%] following placebo), dystonia (n=2 [33.3%] following MK-8189 16 mg), and somnolence (n=2 [33.3%] following MK-8189 16 mg).

2.3 Benefit/Risk Assessment

Participants in clinical studies will not receive direct benefit from treatment during participation as clinical studies are designed to provide information about the safety and properties of an investigational medicine.

No clinical studies with MK-5720 have been conducted to date. The conduct of the proposed clinical first-in-human study described in the clinical protocol is supported by the safety profile of MK-5720 established in the preclinical toxicological studies and that of its

metabolite, MK-8189 in clinical studies. Furthermore, there is no evidence of mutagenicity or genotoxicity in a standard core battery of genetic toxicity assays conducted with MK-5720 and MK-8189.

Additional details regarding specific benefits and risks for participants participating in this clinical study may be found in the accompanying IB and informed consent documents.

3 HYPOTHESES, OBJECTIVES, AND ENDPOINTS

Hypotheses are aligned with objectives in the Objectives and Endpoints table.

The following objectives will be evaluated in participants with schizophrenia.

Primary Objective	Primary Endpoint
To evaluate the safety and tolerability of single-ascending doses of MK-5720 long-acting injectable administered intramuscularly in participants with schizophrenia.	Adverse Events Study discontinuation due to adverse events
To assess the plasma pharmacokinetics of MK-5720 and MK-8189 following single doses of MK-5720 long-acting injectable administered intramuscularly in participants with schizophrenia. <small>CCI</small>	Plasma MK-5720 AUC0-last, AUC0-inf, Cmax, Tmax, CL/F, Vz/F and apparent terminal t1/2 Plasma MK-8189 AUC0-28d, AUC0-inf, Cmax, Tmax, C28d, CL/F, Vz/F and apparent terminal t1/2
To evaluate the safety and tolerability of multiple once-daily oral doses of MK-8189 in participants with schizophrenia.	Adverse Events Study discontinuation due to adverse events
Secondary Objectives	Secondary Endpoints
To assess the plasma pharmacokinetics of MK-8189 following single doses of MK-5720 long-acting injectable administered intramuscularly in participants with schizophrenia <small>CCI</small>	<small>CCI</small>

To compare the effect of the site of administration of MK-5720 long-acting injectable on plasma pharmacokinetics of MK-5720 and MK-8189 following a single dose of MK-5720 long-acting injectable administered intramuscularly in the gluteal muscle relative to its administration in the deltoid muscle.
 
Estimation: The effects of the site of administration on plasma pharmacokinetics of MK-5720 and MK-8189 following a single dose of MK-5720 long-acting injectable administered intramuscularly in the gluteal muscle will be estimated and compared to a single dose of MK-5720 long-acting injectable administered intramuscularly in the deltoid muscle.
	
Plasma MK-8189 AUC0-28d, AUC0-inf, Cmax, Tmax, C28d, CL/F, Vz/F and apparent terminal t1/2
 
Plasma MK-5720 AUC0-last, AUC0-inf, Cmax, Tmax, CL/F, Vz/F and apparent terminal t1/2


Tertiary/Exploratory Objectives
 
Objective: To characterize the morphology of the injection site depot over time, using direct visualization of the depot.
	
Tertiary/Exploratory Endpoints
 
Depot volume and surface area, measured at multiple time points via segmentation of the intramuscular depot on T2-weighted magnetic resonance imaging, after a single dose of MK-5720 long-acting injectable administered intramuscularly in both the deltoid and gluteal muscles.

Objective: To explore the relationship between genetic variation and response to the treatment(s) administered, and mechanisms of disease. Variation across the human genome may be analyzed for association with clinical data collected in the study
	
Germline genetic variation and association to clinical data collected in this study

Objective: To assess the pharmacokinetics of oral MK-8189 following multiple doses of MK-8189 in participants with schizophrenia.
	
AUC0-24, Cmax, Tmax, terminal t1/2, and C24

4 STUDY DESIGN

4.1 Overall Design

This is a randomized, placebo-controlled, multisite, double blind, single ascending dose, parallel group study of MK-5720 in participants with schizophrenia to be conducted in conformance with GCP. The primary objective of the study is to assess the safety, tolerability, and to characterize the PK of single rising doses of MK-5720 administered IM and to evaluate the safety and tolerability of multiple once-daily oral doses of MK-8189 in participants with schizophrenia.

MK-5720-001 clinical study will consist of 6 panels (A, B, C, D, E, and F) and two treatment periods, Periods 1 and 2. Period 1 will include an oral tolerability run-in period with participants receiving once-daily administration of MK-8189 (or corresponding placebo) for 7 days followed by a washout period of at least 72 hours prior to initiation of Period 2. Participants will receive rising single dose IM injection of MK-5720 (or corresponding placebo) in Period 2. The dose of MK-8189 (or placebo) used in Period 1 will vary based on each panel as mentioned in [\[Table 1\]](#). Approximately 8 participants (n=6 for MK-8189/MK-5720 and n=2 for placebo) will be in Panels A and B and approximately 12 participants (n=9 for MK-8189/MK-5720 and n=3 for placebo) in Panels C through F. Each panel will sequentially receive single rising IM doses of MK-5720 and the corresponding dose of oral MK-8189 as mentioned in [Table 1](#). Each participant will be assigned to 1 of 6 panels and will participate in both treatment periods. Participants will be randomized to receive a single IM injection of MK-5720 or placebo and oral MK-8189 or placebo in a blinded fashion. Panels A through C will investigate IM doses of MK-5720 in the deltoid muscle while Panels D through F will investigate IM doses in the deltoid or gluteal muscle based on PK data obtained from Panels A to C. Since patient preference for injection sites differ between geographic regions, the effect of the site of administration of MK-5720 LAI on plasma PK of MK-5720 and MK-8189 following a single dose of MK-5720 LAI administered IM in the gluteal muscle relative to administration in the deltoid muscle will be compared. Currently, the literature on this topic is sparse, but the published data show discrepancies in the elimination half-life, peak plasma concentration, and absorption rate that are dependent on the site of injection. Hence, both PK and safety of MK-5720 LAI will be compared between both IM sites of administration at the highest well tolerated dose of MK-5720 to potentially offer the choice of administration into either the deltoid or gluteal muscle to meet patient and physician preference in future clinical studies. MK-5720 LAI will be administered as a suspension for injection for doses up to ≤ 560 mg that will be administered IM using the appropriate needle size/gauge based on the participant's BMI and site of LAI administration.

MRI exam will be incorporated in 2 panels at or 1 dose level below the highest dose of MK-5720 LAI that are administered IM in the deltoid and gluteal muscles to visualize the injection site depot using multislice spin-echo T2-weighted and assess the location of the depot in the muscle and to quantify drug depot characteristics, including volume and surface area over time. This information will be utilized to better understand any differences in PK between patients and to build models to better predict human PK from preclinical animal models in subsequent clinical studies.

Decision to dose participants with MK-5720 in any given panel will be based on demonstrating acceptable tolerability in individual participants with oral MK-8189 from the oral tolerability run-in period and based on key safety variables including AEs, VS, 12-lead ECGs, laboratory safety tests, neurological and physical examinations, and C-SSRS. The decision for a participant to proceed to Period 2 will be a joint decision between the PI and the Sponsor. Dose escalation decisions for MK-5720 will be based on key safety variables including AEs, VS, 12-lead ECGs, laboratory safety tests, neurological and physical examinations, C-SSRS, and local and systemic reactions assessed in Period 2. The decision to proceed to the next higher dose level will be based upon acceptable safety of MK-5720 at the previous dose. When available, plasma PK data will be reviewed to aid dose escalation decisions. For dose escalation to Panel B, the decision to proceed will be based on 14 days of safety and tolerability data from Panel A. ^{CCI} [REDACTED]

[REDACTED] Plasma concentrations of MK-5720 from the preceding panels will be determined at the allocated PK breaks to ensure that the NOAEL AUC exposure limits are not exceeded at the doses in the subsequent panels. Similarly, plasma concentrations of MK-8189 from the preceding panels will also be determined at the allocated PK breaks to ensure that MK-8189 exposures do not exceed exposures observed with oral MK-8189 at doses that are generally well tolerated in participants with schizophrenia. Dose escalation decisions for Panels C through F will be informed by safety, tolerability, and PK data from all patients in the prior panel through 28 days postdose.

If applicable, participants will be washed off their current antipsychotic therapy prior to MK-8189 dose administration in Period 1. The washout may start with a down titration of the antipsychotic treatment during the screening phase per direction of the investigator. If participants are not currently receiving antipsychotic therapy, they may be domiciled as late as Day -2 prior to dosing administration in Period 1. All participants will be domiciled from the initial washout period prior to dosing MK-8189 in Period 1 and until 28 days postdose for monitoring of safety, tolerability, and intensive PK sampling in Period 2. At the discretion of the investigator, the participants may be domiciled for a longer duration if further observation is required. Participants will return to the clinic for outpatient procedures as outlined in Section 1.3.2 (SoA).

Because this is a Phase 1 assessment of MK-5720 in humans, the PK, pharmacodynamic, and safety profiles of the compound are still being elucidated. This protocol is therefore written with flexibility to accommodate the inherent dynamic nature of Phase 1 clinical studies. Refer to Section 8.10.6 for examples of modifications permitted within the protocol parameters.

Specific procedures to be performed during the study, including prescribed times and associated visit windows, are outlined in Section 1.3 of the SoA. Details of each procedure are provided in Section 8.

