- d. Day 1 Safety Assessments
 1. Predose: VS assessments (HR and BP) and ECG will be completed in triplicate (postdose assessments will be single measurements), RR and orthostatic VS (HR and BP) will be single measurements.
 2. Up to 24 hours: VS assessments (including orthostatic VS) (HR, BP, RR) will be collected at 2-, 6-, and 12-hour postdose in single measurements.
- e. Temperature will be assessed at Screening and Predose Day 1 only and will require single measurements.
- f. Vitals and ECG on Days 2, 4 will be taken only for Panel E and F if the daily MK-8189 oral dose exceeds 24 mg corresponding to MK-5720 dose greater than 280 mg..
- g. The assessment can be done at any time during the day however an attempt should be made for consistent timing across days and periods.
- h. Hematology, chemistry, urinalysis can be use for predose labs in Period 2 as long as they are obtained 24 hours prior to dosing MK-5720.
- i. Additional BARS, AIMS, and SAS assessments should be conducted, as soon as reasonably possible, when there are observed or reported complaints of dystonia and/or akathisia
- j. PK Timepoints for MK-8189
 1. Day 1: predose, 2, 6, 8, 10, 12, and 16 hours postdose
 2. Day 2: 24-hour postdose relative to D1 dose administration
 3. Day 7: predose, 2, 6, 8, 10, 12, 16 hours postdose
 4. Day 8: 24 hours postdose for D7 dose administration
 5. Day 9: 48 hours postdose for D7dose administration
 6. Day 10: 72 hours postdose for D7 dose administration
- k. This sample should be drawn for planned analysis of the association between genetic variants in DNA and drug response. This sample will not be collected at that site if there is either a local law or regulation prohibiting collection, or if the IRB/IEC does not approve the collection of the sample for these purposes. If the sample is collected, leftover extracted DNA will be stored for FBR if the participant (or their legally acceptable representative) provides documented informed consent for FBR. If the planned genetic analyses are not approved, but FBR is approved and consent is given, this sample will be collected for the purpose of FBR.

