4.2 Scientific Rationale for Study Design

The study design selected is deemed optimal for the initial evaluation of safety, tolerability, and PK of MK-5720 in schizophrenic patients.

This is the first instance of administration of MK-5720 to humans with the study aimed to evaluate the safety and tolerability of MK-5720 and characterize the PK profile of MK-5720 as single ascending doses in participants with schizophrenia with the protocol specifically designed in a manner to ensure the safety of the participant. The study incorporates an oral tolerability run-in period with MK-8189 to demonstrate and establish acceptable tolerability with MK-8189 in individual participants prior to administration of MK-5720 IM injection given the inability to reduce daily exposure levels of MK-8189 once MK-5720 injection is administered to participants. Data from the study will be instrumental in guiding dose selection and dosing regimen for future clinical studies. Since the developmental and reproductive toxicological data for MK-5720 has not been generated at this stage, the potential effect of MK-5720 in reproductive healthy women is unknown and hence, only adult men and PONCBP, ages 18 to 60 years of age inclusive, who meet the inclusion criteria are eligible to participate in the study.

The protocol has been designed in a manner to ensure the safety of clinical study participants. In all preclinical studies the bioconversion of prodrug MK-5720 to MK-8189 is rapid and generally similar between monkey and human but found to be more rapid in rat. Following IV administration of MK-5720 in rats and monkeys, the plasma concentration of MK-5720 was undetectable at timepoints beyond 15 minutes postdose. Additionally, the exposure of MK-5720 was less than 1% of the MK-8189 exposure (AUC0-inf) seen after IM administration of MK-5720 in monkeys. The rapid bioconversion prevented determination of t_{1/2} of MK-5720. Given MK-5720 is approximately 650-fold less potent compared to MK-8189 based on in vitro binding assays and that the bioconversion of MK-5720 in humans is anticipated to be rapid, concentrations are expected to be well below pharmacologically active concentrations and therefore, the main pharmacological activity expected in the clinic is as a result of the MK-8189 metabolite. Both, prodrug and MK-8189 concentrations will be actively monitored in the clinic.

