4.3 Justification for Dose

The methods used in calculating doses and estimated exposures are detailed in Section 4.3.1 and Section 4.3.2.

CCI

[figure not shown]

CCI

An oral tolerability run-in period with MK-8189 is included before administration of the IM MK-5720 injection. Due to the short half-life of oral MK-8189 (8-9 h), steady-state plasma exposures are likely to be achieved within the first two days following once daily administration of MK-8189. Hence, MK-8189 will be administered once-daily for 7 consecutive days in the oral-run in period to establish individual tolerability in participants at steady state prior to IM administration of MK-5720.

CCI

As this is a Phase 1 assessment of MK-5720 in humans, and the PK, pharmacodynamic and safety profiles of the compound are still being evaluated, modifications to the dose or dosing regimen may be required to achieve the scientific goals of the study objectives and/or to ensure appropriate safety monitoring of the study participants. Details of allowed modifications are provided in Section 8.10.6.

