9.3 Analysis Endpoints

9.3.1 Primary Endpoints

Safety: Primary safety endpoints will include all types of adverse events and discontinuation of study intervention due to adverse event(s), in addition to laboratory safety tests, ECGs, and vital signs. Baseline is defined as measurements obtained pre-dose Day 1. These endpoints will be calculated for both periods (oral run-in doses of MK-8189 and IM single-ascending doses of MK-5720).

Pharmacokinetics: The pharmacokinetic variables of plasma MK-5720 AUC0-last, AUC0-inf, Cmax, Tmax, CL/F, Vz/F and apparent terminal t1/2 will be evaluated along with the plasma MK-8189 AUC0-28d, AUC0-inf, Cmax, Tmax, C28d, CL/F, Vz/F and apparent terminal t1/2. These PK endpoints apply to Period 2 (IM single-ascending doses of MK-5720).

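### As the Period 1 schedule reads, no laboratory test or physical examination falls between the first oral dose and Day 9, although both feed the depot decision and laboratory tests are a Period 1 safety endpoint

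*Combined protocol and SAP*

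**What the plan says.** Section 4.1 sets the decision to inject MK-5720 on two joined bases. It is "based on demonstrating acceptable tolerability in individual participants with oral MK-8189 from the oral tolerability run-in period", and it is also "based on key safety variables including AEs, VS, 12-lead ECGs, laboratory safety tests, neurological and physical examinations, and C-SSRS". Section 4.2 explains why the run-in exists: "given the inability to reduce daily exposure levels of MK-8189 once MK-5720 injection is administered to participants". Section 4.3 gives the purpose of seven daily doses as "to establish individual tolerability in participants at steady state prior to IM administration of MK-5720", and adds: "Due to the short half-life of oral MK-8189 (8-9 h), steady-state plasma exposures are likely to be achieved within the first two days". Oral dosing runs "for 7 days followed by a washout period of at least 72 hours prior to initiation of Period 2" (Section 4.1).

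Section 9.3.1 counts laboratory tests, ECGs and vital signs among the primary safety endpoints, with baseline at Day 1 predose, and states: "These endpoints will be calculated for both periods (oral run-in doses of MK-8189 and IM single-ascending doses of MK-5720".

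The Period 1 schedule (Section 1.3.1) marks hematology, chemistry and urinalysis at Screening, Day 1 predose and Day 10. It marks the full physical examination at Screening and Day 1 predose. Day 10 of Period 1 is Day -1 of Period 2, and footnote h says: "Hematology, chemistry, urinalysis can be use for predose labs in Period 2 as long as they are obtained 24 hours prior to dosing MK-5720". The next physical examination is the Period 2 predose one (Section 1.3.2).

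**The concern.** The run-in is the last point at which exposure can still be stopped, and it is meant to judge the individual at steady state. Two of the inputs named for that judgment have no scheduled measurement while the participant is taking MK-8189. A laboratory change that tracks drug level and causes no symptoms could appear during dosing, fade in the washout and be absent on Day 10. The participant would then receive a depot with a projected MK-8189 half-life of about 10 days (Section 4.2).

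The endpoint has the same gap. A Period 1 laboratory summary showing no change from baseline would be read as evidence about oral MK-8189, although its only scheduled post-baseline value is taken after the washout.

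**Working it through.** **1. What is scheduled in Period 1 (Section 1.3.1).** Oral dosing is on Days 1–7 and washout on Days 8–10.

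| Assessment | Marks | After first dose, through Day 9 |
|---|---|---|
| Hematology, chemistry, urinalysis | Screening, Day 1 predose, Day 10 | none |
| Full physical examination | Screening, Day 1 predose | none |
| Vital signs, ECG | Screening, Day 1 predose and postdose, Days 2, 3, 4, 6, 10 | Day 1 postdose, Days 3 and 6; Days 2 and 4 only in Panels E and F above 24 mg oral (footnote f) |
| Targeted neurological exam | Day 1 predose, Days 2, 5, 7, 9 | Days 2, 5, 7, 9 |
| BARS, AIMS, SAS | Day 1 predose and postdose, Days 5, 7, 9 | Day 1 postdose, Days 5, 7, 9 |
| C-SSRS since last assessment | Day -2, Day 1 predose, Days 3, 6, 9 | Days 3, 6, 9 |

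AE review runs throughout.

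**2. When the post-baseline assessments fall.** The Day 10 laboratory set is (10 − 7) × 24 = 72 h after the last oral dose, which matches the 72 h in footnote j. Because Day 10 is Period 2 Day -1, an injection on the next day is about (11 − 7) × 24 = 96 h after that dose. With the 24 h predose window in Section 8.10.5, the Period 2 predose physical examination falls at roughly 72–96 h.

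**3. Drug remaining on Day 10.** Fraction = 0.5^(t / half-life). The half-life is 8–9 h in Section 4.3 and 10.9 h in Section 2.2.2.2, which also gives a median Tmax of 10–24 h.

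| Half-life | From dose, t = 72 h | From Tmax 10 h, t = 62 h | From Tmax 24 h, t = 48 h |
|---|---|---|---|
| 8 h | 0.20% | 0.46% | 1.56% |
| 9 h | 0.39% | 0.84% | 2.48% |
| 10.9 h | 1.03% | 1.94% | 4.72% |

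The last two columns are percentages of peak. On every row Day 10 is essentially off drug. Section 4.3.3 intends this, since the washout is there to remove carry-over before injection.

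**4. Drug present 24 h after a dose.** This is the Day 7 predose or Day 8 draw in footnote j. With Tmax at 10 h, t = 14 h and the same formula gives 0.5^(14/8) = 29.7%, 0.5^(14/9) = 34.0% and 0.5^(14/10.9) = 41.1% of peak. With Tmax at 24 h the draw is at peak. Either draw is therefore on drug.

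**5. What the Day 10 set can and cannot show.** The documents give no decay rate for any laboratory effect, so these values are assumptions. If an effect halves every 12, 24 or 72 h after the last dose, the fraction left at 72 h is 0.5^6 = 1.6%, 0.5^3 = 12.5% or 0.5^1 = 50%. Slow effects remain visible; fast ones do not.

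**6. Consequence for the summaries.** The Period 1 laboratory change is Day 10 minus Day 1 predose. If footnote h is used, the Period 2 change is a later value minus that same Day 10 value. No value taken during oral dosing enters either.

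**The case against.** - **Section 4.1 does not require each variable to be measured on drug.** This is correct. A laboratory set after all seven doses and a predose examination satisfy its sentence literally. What remains is the mismatch with the purpose in Section 4.3, which is tolerability at steady state.
- **Day 10 is informative.** A reader might infer that the laboratory tests cannot bear on oral tolerability at all. The documents do not support that: Day 10 follows the full course, precedes injection and shows any change lasting beyond 72 h.
- **The decision is well supplied on drug.** This is true for AEs, vital signs, ECG, targeted neurological examination, EPS scales and C-SSRS, in domiciled participants. None of these measures a clinically silent laboratory change.
- **Extra tests are allowed.** Section 8 and Appendix 2 permit them at the investigator's judgment, and Section 8.10.6 permits changes in timing and tests added to blood already drawn. These are discretionary, and a silent change gives no prompt to use them.
- **No laboratory signal is documented.** This is also true. The common AEs reported for the Phase 2 trial in Section 2.2.2.2 are clinical terms, and detailed data are in the Investigator's Brochure. A reader might infer that participants with a real laboratory effect will be passed for injection; that is a possibility, not something the documents show.
- **The endpoint is modest.** Section 3 lists only AEs and discontinuation, Section 9.5.1 is descriptive, and Section 9.4.1 asks only for one measurement after a dose. This limits the consequence, but Section 9.3.1 still includes laboratory tests for Period 1.
- **The table as read has gaps.** Footnote j requires Day 7 pharmacokinetic samples, but the row shows no Day 7 mark. Section 8.3.7 requires a full neurological examination predose in Period 1, but the row shows Screening only. Footnotes h and j support the Day 10 laboratory set without proving that no other exists, so the marks need confirming.

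**Conclusion.** The point stands in a bounded form. Between the first oral dose and Day 9 the schedule contains no laboratory set and no physical examination. The Day 10 laboratory set is taken with about 0.2–1.0% of drug remaining counted from the dose, or 1.6–4.7% of peak counted from a 24 h Tmax. It can show changes that outlast the washout and cannot show steady-state changes that reverse within 72 h. The Period 1 laboratory endpoint therefore describes the post-washout state, not values during oral dosing.

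It does not follow that the decision to inject lacks on-drug evidence, or that a particular harm will be missed. The conclusion rests on the schedule marks as read and on simple exponential decline at the stated half-lives; it is the same with either half-life. A washout longer than the 72 h minimum would lower the residual further.

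**What to change.** Reconcile Sections 4.1, 4.3 and 9.3.1 with the Period 1 schedule so that at least one hematology and chemistry set is taken on drug. An existing pharmacokinetic draw would serve: Day 7 predose under footnote j, or Day 8 at 24 h after the last dose. Both suit the 8-hour fast that Section 5.3.1.1 requires for laboratory tests. Summarise that set as the on-treatment Period 1 laboratory value, and keep Day 10 as the post-washout value and Period 2 baseline, labelled as such in the Section 9.5.1 summaries. An additional physical examination is not needed for this point, and neither item need leave the Section 4.1 list; the text should say which examination informs the decision.

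The sponsor should first confirm the schedule marks against the source table. Which results bear on the injection decision stays with the sponsor and investigator.

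The cost is a schedule amendment and one extra set of safety tubes at a venepuncture already planned in domiciled participants. The added volume must be checked against the blood-volume limit in the Study Operations Manual.
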